8.5 Patient Characteristics

Baseline patient characteristics will be tabulated, such as demographics (age, race, gender), and disease characteristics.

8.6 Significant Protocol Violations

Significant protocol violations such as with respect to eligibility criteria and treatment plan will be tabulated.

8.7 Concomitant Medications

Drugs that might affect the study medication will be tabulated.

8.8 Exposure and Compliance

Exposure to the study medication will be summarized by frequencies and rates of the doses given. Reasons of not completing all doses will be tabulated.

8.9 Efficacy Analysis

Responses will be tabulated and objective response (CR+PR) via RECIST 1.1 will be summarized with the point estimate and corresponding exact 95% confidence interval. For patients with prostate cancer PSA response ($\geq 50\%$ decline from baseline), PSA progression ($\geq 50\%$ increase from baseline/nadir) and bone lesions progression on ^{68}Ga -PSMA-11 PET or bone scans (≥ 2 lesions from baseline with confirmatory scans 6 weeks later showing ≥ 2 additional lesions) will be reported. Progression free and overall survival will be estimated using standard Kaplan-Meier curves. The median time-to-event for each endpoint will be estimated along with the corresponding 95% confidence interval. Similar descriptive analyses will be performed using irRC criteria. Endpoints such as quantitative characteristics of humoral immune response will be characterized by their mean and corresponding 95% confidence interval. No statistical comparisons are planned. Analyses will be done separately by each expansion cohort. Patients enrolled in the Dose Finding Phase will be excluded when estimating efficacy for the design of a future trial.

8.10 Safety Analysis

Toxicities according to CTCAE 4.0 (see Section 14.2) will be summarized by frequencies and rates calculated as the proportion of patients in the safety population experiencing SAEs, discontinuations due to AEs, and AEs. Two sets of tables will be generated: one for the overall toxicities and one for toxicities related to the study medication (possibly related, probably related and definitely related). Toxicities will be grouped by system using MedRA preferred terminology. Grade 1 to 4 will be reported individually and also as grade 3/4. Deaths will be reported individually. AEs will be reported by dose finding cohort. In the Dose Finding Phase, DLT's will be evaluated in the first 21 days of therapy (see Section

5.2.1.3). The AEs during the expansion phase will also be reported separately by expansion cohort.

Toxicity monitoring in the expansion phase will be continuous with each expansion arm monitored separately. We will consider the treatment to be excessively toxic if the probability of dose limiting toxicities in the first 21 days of therapy is 33% or greater. The following table is based on exact binomial probabilities dropping below 0.10, which we will define as an unlikely possibility:

Stop if number of DLTs is:	3	4	5	6	7	8
in N patients	3	4-6	7-8	9-10	11-13	14-15

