Once the RP2D is identified, the Dose Expansion Phase will be opened. During the Dose Expansion Phase, the study will have a run-in phase with sequential single-agents (Schema B) and then the combination phase (Schema A). The run-in phase may be waived at the investigator's discretion. The reason for the run-in phase during dose expansion is to obtain data on the immunomodulatory effects of vorinostat separately from pembrolizumab. Forty-five patients with prior treatments will be enrolled in three expansion cohorts: 15 anti-PD1 naive renal and urothelial patients, 15 anti-PD1 resistant renal and urothelial patients (defined as patients with transient clinical response or without clinical response to prior immune-checkpoint inhibition), and 15 patients with androgen-sensitive or castration-resistant prostate cancer. The prostate cohort has been added in an amendment during the Dose Expansion Phase, and therefore, will not be part of the Dose Finding Phase.

Anti-tumor activity will be assessed by radiological tumor assessments conducted at baseline, 12 weeks and every 6 weeks thereafter, using RECIST version 1.1 (see Section 14.3). RECIST 1.1 will be used for treatment decisions until first radiologic evidence of progressive disease (PD). Following the first evidence of radiologic PD, treatment decisions may be made by the adaption of RECIST 1.1, termed the immune-related response criteria (irRC) (see Section 14.6) to account for the tumor response patterns seen with pembrolizumab treatment (e.g. tumor flare).

[figure not shown]
1 Cycle = 3 weeks (21 days)

Schema B: Run-In Phase

The RP2D is the dose of pembrolizumab and vorinostat in combination chosen for further clinical development. Further experience in the Dose Expansion Cohort may result in a RP2D dose lower than the MTD.

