5.2.1.3 Definition of Dose-Limiting Toxicity (DLT)

DLTs include any Grade 3-5 toxicity related to vorinostat or pembrolizumab during the combination phase only (Cycle 1) (except for a \ge Grade 3 decrease in lymphocytes). Grade 3 nausea or vomiting should be considered a DLT only if unresponsive to therapy and \ge 72 hours in duration. Patients must have taken at least 4 of the 14 doses of vorinostat to be considered evaluable for DLT determination. Patients who do not complete the first cycle of combination therapy during the dose finding phase will be replaced. Patients who do not receive at least 75% of the expected dose of vorinostat due to toxicity are considered to have DLT. Delay in treatment due to a toxicity greater than 2 weeks is also considered a DLT. ALT $>3\times$ ULN + Total bilirubin $>2\times$ ULN will be a DLT which results in permanent drug discontinuation.

3 patients will be enrolled at dose level 1:

- If 1 DLT occurs in the first 3 patients, expand dose level 1 to 6 patients.
- If 0-1 DLT occur in 6 patients, expand to dose level 2.
- If 1 DLT occurs in the first 3 patients, expand dose level 2 to 6 patients.
- If \ge 2 DLTs occur in the 3-6 patient cohort at dose level 2, the lower dose level will be considered the MDT.
- If \ge 2 DLTs occur in the 3-6 patient cohort at dose level 1, the study will be terminated.

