7.2.1.2 Serious Adverse Event (SAE)

A serious adverse event is any untoward medical occurrence resulting in one or more of the following:

- Results in death or ANY death occurring within 90 days of last dose of study drug (even if it is not felt to be drug related)
- Is life-threatening (defined as an event in which the patient was at risk of death at the time of the event; it does not refer to an event which hypothetically might have caused death if it were more severe)
- Requires inpatient hospitalization or prolongation of existing hospitalization

NOTE: Hospitalizations that are not considered SAEs are:

- Hospitalization planned prior to first administration of study drug
- Hospitalization for elective treatment of a pre-existing condition unrelated to the study medication
- Results in persistent or significant disability/incapacity
- Is a congenital anomaly or birth defect
- Is an important medical event (defined as a medical event(s) that may not be immediately life-threatening or result in death or hospitalization but, based upon appropriate medical and scientific judgment, may jeopardize the patient or may require intervention (e.g., medical, surgical) to prevent one of the other serious outcomes listed in the definition above). Examples of such events include, but are not limited to, intensive treatment in an emergency room or at home for allergic bronchospasm; blood dyscrasias or convulsions not resulting in hospitalization; or the development of drug dependency or drug abuse.
- Pregnancy

- Pregnancy of a patient or of the female partner of a male patient during the study or within 120 days after the last dose of study drug should be reported via an SAE report. Should pregnancy occur in a female participant during the treatment period, study drug should be discontinued and Merck notified immediately. Should a pregnancy occur in a female companion of a male participant during the treatment period, the male participant can continue treatment and Merck notified immediately. Any such pregnancy is to be followed until final outcome. Evaluating Adverse Events
- In addition to the above criteria, AEs meeting either of the below criteria, although not serious per ICH definition, are reportable to Merck in the same time frame as SAEs to meet certain local requirements. Therefore, these events are considered serious by Merck for collection purposes.
 - Is a new cancer (that is not a condition of the study)

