7.2.1.4 Unexpected Adverse Event

An adverse event not mentioned in the Investigator's Brochure or package insert or the specificity or severity of which is not consistent with the Investigator's brochure or package insert.

Refer to Table 6 for additional details regarding each of the above criteria.

Table 6: Evaluating Adverse Events

An investigator who is a qualified physician, will evaluate all adverse events as to:

V4.0 CTCAE Grading	Grade 1	Mild; asymptomatic or mild symptoms; clinical or diagnostic observations only; intervention not indicated.
	Grade 2	Moderate; minimal, local or noninvasive intervention indicated; limiting age-appropriate instrumental ADL.
	Grade 3	Severe or medically significant but not immediately life-threatening; hospitalization or prolongation or hospitalization indicated; disabling; limiting self-care ADL.
	Grade 4	Life threatening consequences; urgent intervention indicated.
	Grade 5	Death related to AE
Seriousness	A serious adverse event is any adverse event occurring at any dose or during any use of pembrolizumab or vorinostat that:	
	†Results in death; or	
	†Is life threatening; or places the subject, in the view of the investigator, at immediate risk of death from the event as it occurred (Note: This does not include an adverse event that, had it occurred in a more severe form, might have caused death.); or	
	†Results in a persistent or significant disability/incapacity (substantial disruption of one's ability to conduct normal life functions); or	
	†Results in or prolongs an existing inpatient hospitalization (hospitalization is defined as an inpatient admission, regardless of length of stay, even if the hospitalization is a precautionary measure for continued observation. (Note: Hospitalization [including hospitalization for an elective procedure] for a preexisting condition which has not worsened does not constitute a serious adverse event.); or	
	†Is a congenital anomaly/birth defect (in offspring of subject taking the product regardless of time to diagnosis); or	
	Is a new cancer; (that is not a condition of the study) or	
	Is an overdose (whether accidental or intentional). Any adverse event associated with an overdose is considered a serious adverse event. An overdose that is not associated with an adverse event is considered a non-serious event of clinical interest and must be reported within 24 hours.	

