9.1 Data Safety Monitoring Committee

The IUSCC Data and Safety Monitoring Committee (DSMC) is responsible for oversight of subject safety, regulatory compliance, and data integrity for this trial. The DSMC will review this study semi-annually to review overall trial progress, toxicity, compliance, data integrity, and accrual per the Institutional DSMP.

Furthermore, the DSMC conducts an administrative review of serious adverse events (SAEs), deviations, reportable events, and any other outstanding business. Major issues may require further DSMC review or action.

For any increase in frequency of grade 3 or above adverse events (above the rate reported in the Investigator Brochure or package insert), the principal investigator will notify the DSMC Chair immediately. The notification will include the incidence of study adverse events, grades, and attributions, as well as investigator statements regarding comparison with risks per the IB/ package insert.

At any time during the conduct of the trial, if it is the opinion of the investigators that the risks (or benefits) to the subject warrant early closure of the study, the DSMC Chair and Compliance

Officer must be notified within 1 business day via email, and the IRB must be notified within 5 business days. Alternatively, the DSMC may initiate suspension or early closure of the study based on its review.

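### The expansion-cohort AE tables in 8.10 do not separate the waivable single-agent run-in from the combination phase, so no combination-period rate is defined

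*Combined protocol and SAP*

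**What the plan says.** Section 3.2 has two secondary objectives, and both concern the safety of pembrolizumab given with vorinostat.

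Section 2.1 says that in the expansion phase "the study will have a run-in phase with sequential single-agents (Schema B) and then the combination phase". It allows the investigator to waive the run-in. The Schedule of Assessments (Section 6.0) shows the run-in as Cycles -2 and -1, and its footnotes limit it to the expansion phase.

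Section 8.10 summarises toxicity by frequencies and "rates calculated as the proportion of patients in the safety population experiencing SAEs, discontinuations due to AEs, and AEs". Section 8.3.2 defines the safety population as all patients with at least one dose of study medication; a combination dose is not required. Dose-finding AEs are tabulated by dose-finding cohort and expansion AEs by expansion cohort. One set of tables covers all toxicities and a second covers those related to study medication. No period is mentioned.

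On severity, 8.10 says "Grade 1 to 4 will be reported individually and also as grade 3/4", and then "Deaths will be reported individually".

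**The concern.** A reader of the expansion tables will want the AE rate of the two drugs given together, since that is what the objectives name and what a later trial would be planned on. Section 8.10 does not define that rate. Three things affect the figure it does define:

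- Events that start on one drug alone are counted with events on the combination.
- Waivers are discretionary, so the share of patients contributing run-in time can differ between cohorts, and part of any difference in AE rates may reflect waivers.
- A patient who stops during the run-in stays in the denominator but cannot contribute a combination event.

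The related-events tables do not resolve this, because relatedness is to study medication and separates neither agent nor period. Elsewhere the protocol does respect the distinction: the DLT definition in 5.2.1.3 counts events in the combination phase only, and 2.1 justifies the run-in by the wish to see vorinostat's effects apart from pembrolizumab.

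A smaller point concerns grades. The only pooled severity row is grade 3/4. By contrast, 5.2.1.3 says "DLTs include any Grade 3-5 toxicity related to vorinostat or pembrolizumab", the notification rule in 9.1 begins "For any increase in frequency of grade 3 or above adverse events", and the vorinostat reference table in 5.2.1.6 pools Grades 3-5 (74.0% for all events, 54.9% for drug-related events). No planned row in 8.10 has that scope.

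**Working it through.** The plan states no expected AE rate, so there is no figure to reproduce. The event rates and the numbers of leavers below are assumptions, chosen to show direction and rough scale.

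**Are run-in events in the data?** Yes. The Schedule of Assessments places an AE review at Cycle -1. Section 7.3.1 starts expedited reporting at the first vorinostat dose. The safety population begins at the first dose of study medication.

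**Share of treatment time.** Two run-in cycles of 21 days give 42 days. This is inferred from the cycle numbering, because the Schema B figure is not shown. With c combination cycles the run-in share is 42/(42 + 21c):

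- c = 3: 42/105 = 40%
- c = 5: 42/147 = 29%
- c = 8: 42/210 = 20%

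These are shares of time, not changes in an AE rate.

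**Pooling the periods.** Let a be the probability of a Grade 3 or higher event on the combination and q the probability of one in the run-in, assumed independent. If every patient has both periods, the pooled proportion is 1 - (1 - a)(1 - q). If half the run-ins are waived, it is the average of a and that value. With a = 33%:

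| q | All have run-in | Half waived |
|---|---|---|
| 5% | 36.4% | 34.7% |
| 10% | 39.7% | 36.4% |
| 20% | 46.4% | 39.7% |
| 30% | 53.1% | 43.1% |

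The combination rate is 33% in every row. Only the run-in rate and the waiver share change.

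**Denominator.** Take 15 dosed patients, 5 of them with an event on the combination. The safety-population rate is 5/15 = 33.3%. If 1, 2 or 3 of the 15 leave during the run-in, the rate among those who started the combination is 5/14 = 35.7%, 5/13 = 38.5% or 5/12 = 41.7%. Sections 5.8 and 8.4 provide for replacing some patients, which would raise the dosed number above 15. If 1 to 3 leavers are all replaced, the contrast is 5/16 = 31.3%, 5/17 = 29.4% or 5/18 = 27.8% against 5/15 = 33.3%.

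**Net direction.** Pooling raises the figure and early leavers lower it, so the documents do not fix the sign of the net difference.

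**Grade 5.** Table 6 defines Grade 5 as "Death related to AE". A patient with a Grade 5 event and no Grade 3/4 event would add 1/15 = 6.7 points to a Grade 3-5 row, for example from 5/15 = 33.3% to 6/15 = 40.0%. If that patient also has a Grade 3/4 event, the change is 0.

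**The case against.** The strongest reply is that 8.10 is a descriptive section of a phase I/Ib trial. It does not label its tables as toxicity of the combination and plans no test between cohorts. The criterion behind the recommended phase 2 dose is the DLT, which is limited to the combination phase and includes Grade 5. Dose finding has no run-in. Section 8.1 also allows further exploratory analyses, so a period split could be made under the current text.

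Most of this stands, and it limits the point to the expansion AE tables for patients who had a run-in. It does not supply the missing rate: being free to run an analysis is not a commitment to report it.

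A second reply is that a split by onset date does not isolate causes. Section 4.2.1 describes target engagement lasting beyond 21 days, and 5.2.1.6 says immune-related events can appear months after the last dose. This also stands. The split describes periods, and the tables should say so.

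Three stronger readings might be inferred, and the documents do not support them:

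- **That fatal events are dropped.** Section 8.10 says "Deaths will be reported individually". The SAE definition in 7.2.1.2 includes an event that "Results in death or ANY death occurring within 90 days of last dose of study drug", so deaths enter the SAE proportion. A patient who dies after a separate Grade 3 or 4 event also remains in the grade 3/4 row.
- **That 8.10 defines severe toxicity as grade 3/4.** It uses no such term; it lists a tabulation.
- **That the combination's rate is overstated.** The effects oppose each other and no rates are given, so no net bias is shown.

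**Conclusion.** The point holds for the expansion cohorts. As written, 8.10 gives a rate over all treatment received by anyone dosed, and no rate for the combination period among patients who received the combination. Dose-finding patients and those whose run-in was waived contribute no run-in events. The 45 planned expansion patients are therefore an upper limit on those affected, before any replacements.

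The size is unknown. The range of 36% to 53% against 33% rests on assumed, independent event rates with every patient having a run-in. The range of 35.7% to 41.7% against 33.3% rests on 1 to 3 of 15 patients leaving during the run-in. Both show what is possible and do not forecast this trial.

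The missing Grade 3-5 row is a minor mismatch with the DLT definition, the 9.1 notification rule and the vorinostat reference table. It is not a loss of fatal events. Neither point affects the DLT criterion in 5.2.1.3.

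**What to change.** In 8.10, keep the overall safety-population tables and add, for the expansion cohorts:

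- AEs with onset in the run-in, by the single agent being taken, among patients who entered the run-in;
- AEs with onset from the first combination dose (Cycle 1 Day 1), among patients who received at least one combination dose;
- the number of patients per cohort whose run-in was waived and the number who left before the combination;
- a note that delayed immune-related events starting in the combination period may reflect earlier single-agent dosing;
- a worst-grade 3-5 row beside grade 3/4, with the individual reporting of deaths unchanged.

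In the same edit, reconcile the expansion monitoring window in 8.10, which refers to the first 21 days of therapy, with the limit in 5.2.1.3 to Cycle 1 of the combination. For a patient with a run-in, the two can be read differently.

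The cost is table programming. Start and stop dates are recorded under Table 6, and grade changes within an episode under 7.2.1.2. The downside is a few more tables with small denominators, so counts should be shown with the percentages.

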8.11 Interim Analysis

No interim efficacy analysis will be performed

9.0 DATA AND SAFETY MONITORING

This study will be conducted in accordance with the IU Simon Comprehensive Cancer Center Institutional DSMP for High Risk Trials.

Investigators will conduct continuous review of data and subject safety. Weekly review meetings for high risk trials are required and will include the principal investigator, clinical research specialist and/or research nurse (other members per principal investigator's discretion). Weekly meeting summaries should include review of data and subject safety by including for each dose level: the number of subjects, significant toxicities as described in the protocol, dose adjustments and responses observed. Study teams should maintain meeting minutes and attendance for submission to the DSMC upon request.

9.1 Data Safety Monitoring Committee

The IUSCC Data and Safety Monitoring Committee (DSMC) is responsible for oversight of subject safety, regulatory compliance, and data integrity for this trial. The DSMC will review this study semi-annually to review overall trial progress, toxicity, compliance, data integrity, and accrual per the Institutional DSMP.

Furthermore, the DSMC conducts an administrative review of serious adverse events (SAEs), deviations, reportable events, and any other outstanding business. Major issues may require further DSMC review or action.

For any increase in frequency of grade 3 or above adverse events (above the rate reported in the Investigator Brochure or package insert), the principal investigator will notify the DSMC Chair immediately. The notification will include the incidence of study adverse events, grades, and attributions, as well as investigator statements regarding comparison with risks per the IB/ package insert.

At any time during the conduct of the trial, if it is the opinion of the investigators that the risks (or benefits) to the subject warrant early closure of the study, the DSMC Chair and Compliance

Officer must be notified within 1 business day via email, and the IRB must be notified within 5 business days. Alternatively, the DSMC may initiate suspension or early closure of the study based on its review.

9.2 DSMC DLT Review

The principal investigator and study statistician will officially review all toxicity for each cohort of subjects prior to making dose escalation/expansion/de-escalation decisions. Once a decision has been reached by the investigator, the official decision and toxicity data will be submitted to the DSMC via email ([contact]). Treating additional subjects may not proceed until official DSMC correspondence confirms approval of dosing decisions for the next stage.

